3 RESEARCH QUESTION/AIM(S)

Our overarching aim is to improve the CAMHS referral process for CYP, their families and carers, as well as for health, education and CAMHS professionals so that CYP receive the help they need as quickly as possible.

Research questions:

1. Using the findings from EN-CAMHS 1 and stakeholder consultation, can we develop a set of national standards for digital CAMHS referral processes?
2. Can we translate the prioritised features from EN-CAMHS 1 of a digitally-led, intelligent CAMHS referral process into a usable, acceptable and widely accessible platform that is nationally standardised, locally adaptable and sustainable?
3. Can we address concerns about digital exclusion and other identified health inequalities through the newly developed CAMHS referral mechanisms?
4. How do referrers, including GPs, school staff and children/young people/families perceive the usability and acceptability of the digital tool?
5. How do referrers use and engage with the tool?
6. How do rates of successful referrals with the tool compare to traditional modes of referral?

There are no primary nor secondary outcome measures for this study as this is a feasibility study to evaluate usage and acceptability of the co-created tool using data collected from referrers. These data will be a combination of quantitative data on usage and engagement and qualitative data from semi-structured interviews with 25 referrers.

3.1 Objectives

1. To develop national standards for digital referrals into CAMHS that have sufficient flexibility to support the diversity of CAMHS configurations locally and regionally (WP1).
2. To co-develop with key stakeholders a standards-compliant digital CAMHS referral tool that maximises the use of digital technologies to support inclusion (e.g. translation support, text to speech, culturally-relevant service information and imagery) (WP2).

3. To implement, test and refine the newly developed standards and digital tool in 5-8 CAMHS providers (WP3), with CAMH sites purposively selected for diverse contextual characteristics.
4. To develop a blueprint for implementation of the new referral process at CAMHS.
5. To develop a robust sustainability plan for standards-compliant CAMHS referral processes so that the platforms developed through the funding remain relevant, usable and useful beyond the lifetime of this grant funding (WP4).

3.2 Outcome

To our knowledge, this is the first study designed specifically to develop a solution to the challenge of rejected/inappropriate CAMHS referrals. Through our extensive consultation with all key stakeholders on the referral process throughout EN-CAMHS 1, we are now positioned to build a solution to the problems of referral that addresses the needs of all types of referrers, including notably young people and their families. Our broad network of collaborators and partners on the project will support widespread dissemination of the work. Our partner MQ will work closely with us throughout the project to ensure that our dissemination, outputs and impact are maximised for the benefit of young people who require mental health support. As in EN-CAMHS 1, we shall leverage our extensive mental health networks to influence and support policy change to bring benefit to CYP and their families through an enhanced referral process. We will aim to share findings as soon as possible and tailor these to the audience. We shall do this through ongoing updates through our social media channels and those of our partners (critically, MQ) and through ongoing presentations, conferences, seminars and informal events across the full lifetime of the project. MQ is our dissemination partner and we shall hold events with stakeholders throughout the project as part of our parallel work on implementation.

The project has the potential for far-reaching and sustained impact. Specifically, we anticipate and will aim for the following effects:

- Reduced proportion of inappropriate referrals to CAMHS.
- Greater proportion of successful referrals.
- Reduced clinical costs for use by CAMHS assessing CYP and families in need.
- Reduced waiting times for first appointments.
- Flattening of recent increases in referral rates.
- Improved quality of referrals and information therein.
- Reduction in length of initial referral meetings.
- Fewer delays in decision-making.
- Improved information about alternative services or self-help.
- With swifter processes, it will help reduce the number of young people who get to assessment stages and then get rejected for becoming eligible for adult services [9].
- Improved patient experience through transparency of progress during referral.
- Potentially more time made available for face to face appointments when needed due to more efficient and complete referral process.
- In services where dedicated time to discuss referrals are not routine, greater availability can be carved out for direct contact (phone, email) to prevent inappropriate and rejected referrals, and to ensure those CYP who need be seen do so. This remains an essential clinical activity to ensure patient safety. It would reduce the need for lengthy, and weekly referral meetings freeing up resource internally.

- Having the necessary sources of information and complete investigations prior to the initial assessment will improve throughput and waiting times within the CAMHS system leading to increased patient and clinician satisfaction and earlier interventions/diagnosis as appropriate. Clinicians would be freed up from chasing further information to supplement their assessment and formulation and this will improve efficiency and release their time for clinical duties.
- We shall facilitate NHS England's ability to benchmark and monitor referrals into CAMHS and the information from the digital referrals process will also aid ICBs to commission services best suited to support local need.
- We shall influence policy and practice through direct contact with NHS partners and governments and by feeding information about referral over time and different regions. Many of our project team and collaborators are influencers at national and regional policy level (e.g. [name]; [name]; [name]; [name]). We shall also input directly to professional groups (e.g. Faculty of Child and Adolescent Psychiatry).

4 STUDY DESIGN and METHODS of DATA COLLECTION AND DATA ANALYSIS

The study uses a mixed method design, including:

- Extensive stakeholder consultation relating to design information for the digital tool through focus groups, workshops and semi-structured interviews (Qualitative). Analysis of how people use and engage with the newly developed CAMHS referral tool (Quantitative – engagement and usage metrics; qualitative – semi-structured interviews).
- Analysis of successful referral rates compared to traditional modes of referrals.
- Designing, developing and testing a digital referral tool using Agile approaches.

4.1 Data Collection

Work Package 1 (WP1), Months 3-12 (Leads: MQ, PW, PB) - Requirements Prioritisation

Aims:

- We shall hold 2 x roundtable events (Manchester and London) to gather feedback and input from senior stakeholders (e.g. NHS England senior leaders; commissioners, CAMHS leaders).
- With our partner MQ, we shall conduct 6 stakeholder focus groups with CYP, families/carers and professionals including GPs, to collaboratively prioritise requirements (identified in EN-CAMHS 1) for the revised digital tool. We aim to recruit up to 10 stakeholders per group, therefore 60 participants in total. We shall use the MoSCoW prioritisation method [29] collaboratively as we have done in a number of other NIHR funded digital health projects. As part of this prioritisation process, each of the existing 11 interactive CAMHS referral forms created by individual CAMHS in England will be rated using the System Usability Scale [30] and using criteria from the EN-CAMHS 1 focus groups (e.g. navigability, clarity of language, accessibility).

The technical project team will use the information from the roundtable and stakeholder meetings about the broader technical mental health landscape alongside their expert digital health software knowledge to develop a set of technical standards relevant for the CAMHS referral process. The costed software engineer will align with and extend existing NHS referral standards and interoperability standards to achieve this aim.

Work Package 2 (WP2) (PW, RE, JEC, Digital Health Software Team, VB): Months 3-12 - Co-Design and Tool Implementation

Aims:

- Onboard 5-8 CAMHS providers (with different characteristics and served populations) who are willing and can support an evaluation of the digitally-enhanced CAMHS tool in collaboration with our partners, NHS England.
- Workshops with 5-8 Trust staff from each provider.
- Co-design the tool with CAMHS stakeholders (2 x 1-hour workshops with 25 referrers).
- Ensure accessibility support (WCAG2.2 and assistive technology, translations of the tools etc) is extensive and supports needs identified by stakeholder consultation (Digital Accessibility Working Group n=10) and in collaboration with PPIE, YPAG and PPAG. This group will be formed from the project with characteristics derived from accessibility needs identified in the stakeholder codesign groups and from ENCAMS 1. This group shall meet twice during the co-design process to review the tool and suggest accessibility enhancements. Every effort will be made to incorporate suggestions made by this group into the digital tool.

National and locally relevant content (e.g. links to alternative sources of help) will be developed in collaboration with CAMHS professionals at each of the providers and in collaboration with the CAMHS professionals on our research team. We shall run a workshop at each of the chosen providers with 5-8 Trust staff members from different departments, for example, clinical IT, digital strategy, CCOs, research. These workshops will undertake a full assessment of the capability of the Trust to implement, identify risks to implementation, and create a plan to manage and mitigate them. We have costed a professional content designer to ensure the quality and accessibility of content developed. We have provisional confirmation from the following CAMHS providers for WP2 and WP3: Manchester University NHS Foundation Trust (South Manchester, North Manchester); Greater Manchester Mental Health NHS Foundation Trust (Bolton, Wigan); East London NHS Foundation Trust (South Bedfordshire and Luton).

Our team has worked across many NIHR funded digital mental health projects. We shall use the same approach in this project, developing with an iterative Agile and a user-centred design approach to co-develop the platform. This approach enables the software team to work closely with and respond to the needs of the end user. This will be delivered through (a) user research (b) moderated usability testing with end users. This design approach will follow the below stages:

- Discovery [38]: The discovery phase will draw heavily on the findings of ENCAMS 1 and of Work Package 1 of this project. We shall translate these findings into outputs that can be disseminated widely including User Personas (to indicate the profiles of different referrers who will use the system) and User Journey Maps (to show how people will interact with the system at each stage of the process).
- Alpha [39]: Our senior designer will produce prototypes and wireframes to demonstrate the flow of the digital tool in this phase for feedback and review by workshop participants.
- Beta [40]: During this phase, we shall ask at least 5 healthy volunteers to try out the newly-developed tool to ensure it has no critical or major defects and is ready for use in the evaluation in WP3.
- Live [41]: The live version of the platform will be demonstrated in a co-design workshop available for participants to try and provide feedback.

A priority for the digital tool is to be inclusive and accessible to all. We will work collaboratively with our stakeholder groups during the co-design phase to ensure we maximise the accessibility of the tool. From EN-CAMHS 1 we already know that supporting access to translated materials is an important requirement. We aim to go well above and beyond the WCAG 2.2 standards [31] to ensure that the tool we develop has as wide a reach as possible. We shall also beta-test the accessibility with a Digital Accessibility Working Group.

Work Package 3 (WP3): (KMA, PW, VB, LAC, PB, RE, PB) Months 12-24 - Evaluation of Implementation

We aim to:

- Evaluate implementation of the new digitally-enhanced referral process with 60 key referrers.
- Explore the potential, enablers and barriers of embedding a new CAMHS referral mechanism via semi-structured qualitative interviews with 25 referrers.
- Develop a blueprint and toolkit for CAMHS to implement the referral tool.
- Understand if and how the tool enhances the CAMHS referral process.

A mixed-methods, non-randomised evaluation of implementation with 60 CAMHS referrers across 5-8 CAMHS. CAMHS sites and referrers will be chosen to reflect the diversity of the current CAMHS landscape. 9 CAMHS sites have indicated their support for working with us on the evaluation. We shall evaluate usage and acceptability data collected from referrers which combine quantitative data on engagement and usage with qualitative data from semi-structured interviews with 25 referrers.

We shall use the NASSS-CAT toolkit [32] to guide the implementation and evaluation of the digital tool across CAMHS sites. This entails running a NASSS-CAT workshop with key stakeholders from each CAMHS service in order to introduce and complete the assessment as well as create a risk management and mitigation plan. The workshop will identify gaps in information that will need to be identified and incorporated. Once this is done, the risk plan will be regularly reviewed throughout the implementation process. Insights from this will be turned into an implementation toolkit that sets out a standardised evidence-based approach along with common risks and how they can be managed or mitigated. We shall also use the NASSS-CAT implementation toolkit to explore the potential, enablers and barriers of embedding a new CAMHS referral mechanism across different types of referrers and across CAMHS with various configurations. The NASSS-CAT toolkit will be used to guide implementation discussions with key stakeholders. Specifically, we will use the NASSS framework to address key considerations for the implementation digital transformation covering the key NASSS areas: the illness/condition in question; the technology; the value proposition; the intended adopters; the organisation; external context for innovation. The questions from the NASSS-CAT toolkit on these areas will be tailored for the EN-CAMHS project and used to structure the topic guides for interviewers with referrers.

We shall collect referral data from each referrer and from the CAMHS site referred into. We shall collect number of referrals made via the digital tools and numbers made by traditional referral mechanisms. We shall collect usage and engagement data with the tool, including numbers of referrals completed to an endpoint (either referral sent to CAMHS or to alternative help). We shall collect data on accepted/rejected referrals made by participant referrers to CAMHS using a) the tool and b) traditional modes of referral. Co-design workshops with each CAMHS provider will help us understand which data can be captured, and how each provider records the data.

We shall conduct semi-structured qualitative interviews with 25 referrers (including CYP and their families/carers as well as professional referrers) to understand the usability and acceptability of the new referral process. Interview schedules will be developed in collaboration with our YPAG and PPAG to explore experiences of using the new referral process: usability, content quality, barriers/enablers and any future refinements. The interview schedules will be informed by two recognised theoretical frameworks to assess intervention development, implementation and sustainability (NASSS, NPT [33]) and will focus on how the intervention becomes/does not become incorporated and sustained in practice. We shall use the mechanisms defined by NPT (coherence, cognitive participation, collective action and reflexive action) to structure the topic guides for interviewers with referrers. This will enable us to explore and analyse the implementation of the digital tool collaboratively. Interviews will be conducted by a Research Associate trained and experienced in qualitative methods. Consenting participants will be interviewed for up to one hour at a convenient location and transcribed verbatim.

Work Package 4, (WP4): (MQ, KMA, PW) Months 6-30 - Sustainability Planning

The charity MQ Mental Health Research was a key partner to EN-CAMHS 1. We plan to continue this successful partnership in EN-CAMHS 2. In this WP4, MQ will drive the sustainability of the EN-CAMHS tools. MQ are actively engaged in discussions with the Prudence Trust about longer-term sustainability support for the platform. MQ aim to collaborate to drive and support the tools' implementation, nationally if possible. This will require lobbying key national stakeholders (including senior policymakers, regional ICB leads, mental health professional bodies) to support implementation of the platform for the medium and longer terms, beyond the lifetime of this grant. MQ have secured funding from the Prudence Trust to support longer term sustainability for the referral tool and enhanced referral processes developed through this project. MQ will work to secure alternative longer term sustainability solutions through a piece of work called 'FORESIGHT' which will be delivered in three overlapping phases, complementing deliverables within EN-CAMHS 2.

PPIE

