8.2 Outputs

Key indicators of success will be defined by the following criteria:

- Digital referral platform successfully tested across minimum 5 CAMHS.
- Stakeholders successfully recruited to roundtable events and prioritisation of features consultation.
- CAMHS referral technical standards defined.
- Co-design of digital tool completed with outputs produced and published.
- Quantitative referral data collected and analysed from CAMHS sites. A reduction in the proportion of unsuccessful referrals is achieved when made through the ENCAMS platform compared to the usual referral processes.
- Following AMUsEd framework, engagement and usage metrics with the digital platform demonstrate that the platform is usable and acceptable to referrers.
- Qualitative intervention data successfully collected and analysed. Qualitative interviews demonstrate usability and acceptability of the platform to referrers and key stakeholders, including GPs, school staff, health and educational professionals and CYP and families/carers themselves. Qualitative interviews demonstrate a preference for the platform by referrers and key stakeholders, including GPs, school staff, health and educational professionals and CYP and families/carers themselves.
- Evaluation successfully completed.
- Sustainability plan developed that secures future plan for the CAMHS digital tool supported for use within the NHS.

Specific outputs for WP1

- Report detailing the changing CAMHS landscape (from roundtables) and how the digital tool aligns with newly configured CAMH services.
- Clear set of priorities and requirements for the revised CAMHS referral process, ranked by Must Have, Should Have, Could Have and Won't Have (MoSCoW) to enable the technical build in Work Package 2.
- A set of technical referral standards for the digital tool for development in WP2.

Finally, we aim to produce 4 peer-reviewed academic publications during the project.

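### No standardised usability measure is planned for the new tool, and usage metrics are counted as evidence that it is usable

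*Protocol*

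**What the plan says.** The System Usability Scale (SUS) is planned in Protocol section 4.1, under WP1, where "each of the existing 11 interactive CAMHS referral forms created by individual CAMHS in England will be rated using the System Usability Scale". The rating is introduced with the words "As part of this prioritisation process", so its stated job is to inform the requirements for the new tool.

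Research question 4 (section 3) asks how referrers "perceive the usability and acceptability of the digital tool". Research question 2 asks whether the tool can be made usable. Research question 5, listed separately, asks how referrers use and engage with it.

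For the new tool, the WP3 data in section 4.1 "combine quantitative data on engagement and usage with qualitative data from semi-structured interviews with 25 referrers". The interviews are held "to understand the usability and acceptability of the new referral process". Section 8.2 then gives two indicators of success that concern usability:

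- Under the AMUsED framework, "engagement and usage metrics with the digital platform demonstrate that the platform is usable and acceptable to referrers".
- Separately, "Qualitative interviews demonstrate usability and acceptability of the platform to referrers and key stakeholders".

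**The concern.** The protocol treats perceived usability and use as different questions, yet one indicator in 8.2 takes data on use as proof of usability and sets no threshold. Logs record what was opened, completed and submitted. They do not record how hard it was. A referrer with a duty to refer may finish the form whether it was easy or laborious.

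This matters because section 3 describes a feasibility study of usage and acceptability, and two of the six research questions name usability. If the indicator stands, the study could report a quantitative demonstration of usability without having measured it. The only direct user reports in WP3 would come from the interviewed minority. The gap lies in data collection, so an analysis plan written later cannot close it.

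**Working it through.** The protocol gives no SUS target, standard deviation or margin, and section 6.3.1 states that no power calculation was used. There is no stated figure to reproduce. The check is a reading of the text followed by simple counts.

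**1. Where the SUS appears.** It appears once in the body (section 4.1, WP1, for the 11 existing forms) and once in the reference list.

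**2. Whether another usability scale is planned for the new tool.**

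- WP2 (4.1): moderated usability testing is part of development, with no instrument named. The Beta stage uses at least 5 healthy volunteers to look for critical or major defects.
- WP3 (4.1): counts of referrals by route, accepted and rejected referrals, usage and engagement data, and interviews. No scale.
- Analysis (4.2): usage summarised over time and explored by referrer type, effective engagement, rate of successful referrals, framework analysis of transcripts. No usability score.
- Appendix 1: the only questionnaire is on demographics.
- Appendix 2: consent, demographics, focus group, workshops, interview. No scale.

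**3. Which data answer which question.**

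| Question | Direct evidence planned in WP3 |
|---|---|
| RQ4, perceived usability and acceptability | Interviews with 25 referrers |
| RQ5, use and engagement | Logs for the 60 referrers |

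The AMUsED indicator in 8.2 applies the evidence in the second row to the question in the first.

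**4. Counts.** Section 6.2.1 gives 60 referrers using the tool, of whom 25 are interviewed.

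- Users giving a standardised usability score: 0 of 60.
- Users with no planned usability self-report in WP3: 60 − 25 = 35, and 35/60 = 58%.

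**5. What a score from all 60 would give.** The half-width of a 95% confidence interval for a mean is t × SD/√n. With n = 60 and t ≈ 2.00, this is 2.00/√60 = 2.00/7.75 ≈ 0.26 SD. It assumes that all 60 respond and that clustering by site is ignored. Non-response or clustering would widen it. This is adequate for a descriptive overall score and needs no hypothesis test.

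**The case against.** The strongest reply is that usability is already assessed in several ways. The interviews have usability as their stated purpose and are an explicit second basis in 8.2. WP2 adds moderated usability testing, two accessibility reviews and feedback on the prototype and live versions. RQ4 asks about perception, which interviews can answer, and interviewing 25 of 60 is an ordinary subsample in a feasibility study without primary or secondary outcomes. The logs are also not blind to a laborious tool. Traditional routes stay open (section 2), and WP3 counts each referrer's referrals by both routes, so a drift back to the old route or a failure to reach an endpoint would show.

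Much of this stands. It rules out two stronger readings that a reader might infer:

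- **That the usability claim rests on logs alone.** Sections 4.1 and 8.2 rest it on the interviews as well.
- **That the WP1 ratings are a benchmark the study set itself and then failed to use.** Section 4.1 gives their purpose as prioritisation, and no SUS comparison between the tool and the 11 forms is promised. The comparison promised in RQ6 concerns referral success.

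The reply does not rescue the AMUsED indicator. WP2 testing serves development and does not measure usability among the 60 evaluation users. Return to traditional routes is indirect evidence, bearing on acceptability more than on perceived ease of use. The 58% is a count of people not asked and does not measure bias.

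**Conclusion.** The point holds as a gap in measurement, together with one indicator that claims too much. The study uses a short usability scale on other people's forms and plans none for its own tool, so its only quantitative evidence on usability is data on use. The study can run as written and the interviews will inform RQ4. The change is nevertheless worth making, because it is cheap and has to be in place before WP3 use begins.

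This rests on the protocol text alone. It assumes that no usability scale is planned in a study document not shown here, although Appendix 1 lists none.

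A reader might also infer that SUS scores for the tool would be directly comparable with those of the 11 forms. The documents do not support that. Section 4.1 does not clearly say who rates the forms, and scoring 11 forms in a prioritisation exercise differs from scoring one tool after a live referral. Matching the raters may no longer be possible: the study began on 01/06/2024, WP1 runs over months 3-12, and version 2.2 is dated 31/03/2025, the end of month 10.

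**What to change.** - **Sections 4.1 and 4.2, WP3:** show the SUS on screen to all 60 referrers after their first referral with the tool, whether completed or abandoned. Report the number who answered and the overall score with its confidence interval. Give scores by referrer type descriptively only, since a purposive sample of 60 weighted towards GPs leaves small groups.
- **Section 8.2:** base the quantitative usability indicator on this score, read alongside the interviews. Keep the AMUsED metrics as evidence of engagement and uptake.
- **WP1 scores:** show those of the 11 existing forms as descriptive context, stating who rated them and in what setting. Claim no direct comparability unless raters and setting match.

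The cost is one short questionnaire per participant, a small addition to the tool, and an update to the participant information. Section 6.3.2 already places the information sheet and consent form inside the tool, so the route exists. No extra participants or staff are needed. The downside is brief added burden for respondents.
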